7 HOLDING RULES AND SAFETY MONITORING

7.1. No group holding rules will be pre-defined considering the evidence for a favourable safety profile of this candidate vaccine in Phase III infant evaluation.

7.2. Individual subject holding rules. Individual study participants who present at least one of the following stopping rules for individual subjects will be withdrawn from further vaccination:

- a) Local reactions: upon investigator discretion.
- b) Systemic solicited adverse events: The subject develops a Grade 3 systemic solicited adverse event beginning within 2 days after vaccination (day of vaccination and one subsequent day) and persisting at Grade 3 for >2 consecutive days.
- c) Unsolicited adverse events: The subject has any Grade 3 adverse event considered related to vaccination, persisting at Grade 3 for >2 consecutive days.

- d) The subject has a serious adverse event considered related to vaccination.
- e) The subject has an acute allergic reaction or anaphylactic shock following the administration of vaccine investigational product.
- f) Laboratory adverse events: The subject has any Grade 3 laboratory adverse event considered related to vaccination.

7.3. Safety Oversight

7.3.1. Medical Monitor

A Medical Monitor, representing the Sponsor will be appointed for oversight of safety in this clinical study. The Medical Monitor will be responsible for safety assessments as outlined below. The monitor will review the study prior to initiation and will be available to advise the Investigators on study-related medical issues and to act as a representative for the welfare of the subjects. The monitor does not have direct involvement in the conduct of the study and does not have other interests with any collaborating pharmaceutical firms or their competitors. All serious adverse events and any AEs that fulfil the criteria for pausing or halting will be reported to the medical monitor within 24 hours of becoming aware of the event. The monitor is responsible for the review of the safety data and communicate with the PI and/or the DSMB, as appropriate.. The Medical Monitor may also provide recommendation for continuation, modification, or termination of the study, if there is urgent need.

7.3.2. Data and Safety Monitoring Board

The DSMB will review the study prior to initiation; review the interim safety data reports; and review all SAEs at the end of the study. The Board may convene additional reviews if deemed necessary, on review of the safety data, as sent, periodically by the Medical monitor. All SAEs will be reported by the PI to the DSMB at the same time they are submitted to the IRB. The PI will notify the Board at the time pausing or halting criteria are met and obtain a recommendation concerning continuation, modification, or termination of the study. The PI will submit the written DSMB summary reports with recommendations to the IRB(s).

8 STATISTICAL ANALYSIS

8.1 Endpoints

We will assess the RTS,S recipients with regards to:

- Safety: the occurrence of AEs and SAEs (please see safety section)
- Immunogenicity: serum anti-CS antibody titre responses and anti-CS antibody avidity.

8.2 The Number of Participants

The sample size calculations are based on the objective of comparing the serologic response to RTS,S/AS01E vaccine co-administered with DHA-PIP + SLD-PQ with RTS,S/AS01E or RTS,S/AS01B vaccine alone in adults. This is a phase II trial. Sample sizes for phase II trials are usually small, as safety is still of paramount importance. Valid sample sizes for comparing sample sizes between two groups are usually obtained using exact test methods such as the Fisher's exact test power calculations. This is done using simulations as sample size formulas are not well developed. To estimate the sample size we use a four-fold increase in anti-CS antibody titre as an assumed correlate of protection. For the sample size calculation, we assume that the background rate of response in the reference groups will be 5% and the true rate of anti-CS antibody response in the vaccine groups is 80%. We wish to exclude, for the vaccine, a one-tailed lower 95% CI for the reference-vaccine group difference of lower than 30%. The study aims to detect this difference with 90% power (because the detectable difference is big) and testing at 5% significance level. With these assumptions, and using the method of Blackwelder[37] for precision-based sample size calculations, a total of 20 participants per group would be needed for arms 1 and 2 because the anticipated difference is too big. However, for arms 3 to 7 (Table 3 below), we will need more participants per group because a smaller detectable effect is anticipated. Using the Fisher's exact test power simulations, a difference in serologic response of 30% (say 65% vs 95%) gives approximately 80% power with a sample size of 30 participants in each group testing at 5% significance level. Therefore the total sample size for all the 7 arms will be 190 participants.

The size of study groups is relatively small hence it is imperative to minimise potential losses. Whenever possible an attempt will be made to replace study participants should a participant be withdrawn or choose to withdraw. The stata command for obtaining the Fishers exact test power simulations is: `power two proportions 0.65 0.95, test(fisher) n1(30) n2(30)`. This has been performed in Stata 14.

The required sample sizes are summarized as follows:

Table 3: Sample size and vaccine vials required for each arm

Group	# participants	Vaccine	Dose M0	Dose M1	Dose M2	Antimalarial	vaccine vials required
1	20	RTS,S/AS01B	Single standard dose (0.5mL)	Single standard dose (0.5mL)	Fx dose (0.1mL)		60
2	20	RTS,S /AS01E	Double standard dose (1.0mL)	Double standard dose (1.0mL)	Double Fx dose (0.2mL)		60
3	30	RTS,S/AS01E	Single standard dose (0.5mL)	Single standard dose (0.5mL)	Single standard dose (0.5mL)		90
4	30	RTS,S/AS01E	Single standard dose (0.5mL)	Single standard dose (0.5mL)	Single standard dose (0.5mL)	DHA-PIP+PQ	90
5	30	RTS,S/AS01E	Single standard dose (0.5mL)	Single standard dose (0.5mL)	Fx dose (0.1mL)		90
6	30	RTS,S/AS01E	Single standard dose (0.5mL)	Single standard dose (0.5mL)	Fx dose (0.1mL)	DHA-PIP+PQ	90
7	30	RTS,S/AS01E	Single standard dose (0.5mL)		Fx dose (0.1mL)	DHA-PIP+PQ	60
Total	190						540

Fx dose= fractional dose

RTS,S/AS01B = adult formulation containing 50µg of RTS,S and 50µg MPL and 50µg QS-21 in the standard dose of 0.5mL.

RTS,S/AS01E = standard formulation containing 25µg of RTS,S and 25µg MPL and 25µg QS-21 in the standard dose of 0.5mL.

DHA-PIP = dihydroartemisinin-piperaquine

PQ = single low dose primaquine

Fx dose = fractional dose i.e. 1/5th of standard dose of RTS,S/AS01B or RTS,S/AS01E

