3 OBJECTIVES

The trial has the following objectives:

- To assess the safety and immunogenicity of the **standard formulation** of the RTS,S vaccine (RTS,S/AS01E) in Thai adults (Group 3 alone).
- To assess the safety and immunogenicity of the **adult** formulation of the RTS,S vaccine (RTS,S/AS01B) in Thai adults (Group 1 alone).
- To compare the safety and immunogenicity of a fractional dose RTS,S regime (where the third dose is a 1/5th of the standard dose) using the **adult formulation** (RTS,S/AS01B) to the safety and immunogenicity of fractional dose RTS,S regimes using either single or double doses of the standard formulation (RTS,S/AS01E), in Thai adults (Group 1 vs Group 2 and Group 1 vs Group 5).
- To compare the safety and immunogenicity of fractional dose regime (where the third dose is a 1/5th of the standard dose) using a single dose of the **standard formulation** (RTS,S/AS01E) to the safety and immunogenicity of fractional dose RTS,S regime using a double dose of the standard formulation (RTS,S/AS01E), in Thai adults (Group 2 vs Group 5).
- To compare the serologic response to RTS,S/AS01E vaccine when co-administered with DHA-PIP + SLD-PQ with RTS,S/AS01E vaccine alone in adults, when RTS,S/AS01E is given in either a fractional dose regime (where the third dose is a 1/5th of the standard dose) or a full standard dose regime (Group 3 vs. Group 4 and Group 5 vs Group 6).
- To compare the serologic response to RTS,S/AS01E vaccine co-administered with DHA-PIP + SLD-PQ, when RTS,S/AS01E is given in a fractional two-dose regimen (Month 0, standard dose and Month 2, fractional (1/5th) dose) with RTS,S/AS01E vaccine co-administered with DHA-PIP + SLD-PQ, when RTS,S/AS01E is given in a fractional three-dose regimen (Month 0 and Month 1, standard doses and Month 2, fractional (1/5th) dose) (Group 6 vs Group 7)

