4.2 Primary Outcome Measures

The primary outcome measures will be:

- The safety of the investigational vaccine in each group:
 - Occurrence of serious adverse events (SAEs) from the date of the first vaccination to 29 days after the last vaccination, according to the MedRA classification.
 - Occurrence of SAEs during the whole study period, i.e. during a 6 month follow up period from the receipt of first vaccination, according to the MedRA classification.

- For groups 1 to 6, the concentration of antibodies against *Plasmodium falciparum* circumsporozoite (anti-CS antibody), one month after the first dose (at Study month 1), one month after the second dose (at Study month 2), one month after the third dose (at Study Month 3) and six months after the first dose (at Study Month 6).
- For group 7, the concentration of antibodies against *Plasmodium falciparum* circumsporozoite (anti-CS antibody), one month after the first dose (at Study month 1), two months after the first dose (at Study month 2), one month after the second dose (at Study month 3), and six months after the first dose (at Study Month 6).

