enrolment evaluation. In such cases, these tests (parasite microscopy, haemoglobin, biochemistry, and urine pregnancy test) would not need to be repeated at the baseline (Month 0 / Day 0) visit. If all inclusion criteria are fulfilled and none of the exclusion criteria apply, the patient will be enrolled into the study and a CRF specific to each participant completed. Regimen allocation and administration of the vaccine(s) will be on Day 0. The randomization lists will be prepared by MORU.

Randomization numbers will be generated in blocks, for the 7 intervention arms in a ratio of 20:20:30:30:30:30:30, as follows:

- RTS,S/AS01B Fractional dose group (Group 1)
- Double RTS,S /AS01E Fractional dose group (Group 2)
- RTS,S/AS01E Standard dose group (Group 3)
- RTS,S/AS01E + DHA-PIP+PQ Standard dose group (Group 4)
- RTS,S/AS01E Fractional dose group (Group 5)
- RTS,S/AS01E + DHA-PIP+PQ Fractional dose group (Group 6)
- RTS,S/AS01E + DHA-PIP+PQ Fractional two-dose group (Group 7)

Study participants will be assigned the next available randomization number on the list, and thus will be randomly allocated to Group 1, 2, 3, 4, 5, 6 or 7. This is an open-label study and participants and clinical investigators will not be blinded to group allocation.

Subjects will then be vaccinated by intramuscular (IM) needle injection into the deltoid region of the arm. Subjects in Groups 4, 6 and 7 will also receive anti-malarial medications.

The study participants will be observed closely for at least 30 minutes following the administration of each study vaccine, with appropriate medical treatment readily available in case of an anaphylactic reaction.

An oral thermometer, tape measure and a paper diary card for solicited AEs will be given to each participant along with the emergency 24 hour telephone number to contact the on call study physician if needed. Diary cards will collect information on the timing and severity of the following solicited AEs:

Local solicited AEs	Systemic solicited AEs
Pain at injection site	Fever
Redness at injection site	Gastrointestinal symptoms (nausea, vomiting, diarrhoea and/or abdominal pain)
Swelling at injection site	Fatigue
	Headache

Participants will be instructed on how to self-assess the severity of these AEs. There will also be space on the diary card to self-document unsolicited AEs, and whether medication was taken to relieve the symptoms.

4.8.5 Subsequent vaccination visits (Month 1 / Day 0 and Month 2 / Day 0 visits)

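### The 20 per arm and 90% power for arms 1 and 2 rest on a comparison with a 5%-response group that the trial does not contain

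*Protocol*

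**What the plan says.** Section 8.2 (The Number of Participants) opens by tying the sample size to the comparison of vaccine given with antimalarials "with RTS,S/AS01E or RTS,S/AS01B vaccine alone in adults". The response is a four-fold rise in anti-CS titre. For the first calculation it states "we assume that the background rate of response in the reference groups will be 5" per cent, takes 80% as the true rate in the vaccine groups, and asks that a one-tailed 95% lower bound for the difference between the two exclude 30 points. The power is set at 90% and the significance level at 5%. Citing a Blackwelder method, it concludes that "a total of 20 participants per group would be needed for arms 1 and 2 because the anticipated difference is too big". A second calculation, for arms 3 to 7 only, uses 65% v 95% with 30 per group and reports about 80% power.

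The design is set out elsewhere. Section 4.8.4 randomises "for the 7 intervention arms in a ratio of 20:20:30:30:30:30:30", and Table 3 and Appendix A give RTS,S to every arm. Section 3 uses arms 1 and 2 for "Group 1 vs Group 2 and Group 1 vs Group 5", and then for Group 2 v Group 5. It lists the antimalarial comparison as "Group 3 vs. Group 4 and Group 5 vs Group 6". The primary immunogenicity outcome in section 4.2 is a continuous measurement: "For groups 1 to 6, the concentration of antibodies against" the circumsporozoite protein at four time points.

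**The concern.** A 5% response rate could describe people who have not been vaccinated, and the trial has none. Every comparison involving arm 1 or arm 2 sets one RTS,S regimen against another, where nothing in the protocol leads one to expect a 75-point gap. Section 8.2 itself gives arms 3 to 7 more participants because it expects a smaller effect there. That reasoning applies equally to the contrasts of arms 1 and 2, two of which use Group 5, one of those larger arms.

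The opening objective does not fit either. Neither arm 1 nor arm 2 receives antimalarials, and section 3 places neither in the antimalarial comparison.

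The only power stated for arms 1 and 2 thus belongs to a comparison that cannot be made. A reader or oversight body could carry the 90% over to the formulation comparisons and take a non-significant result as evidence that the regimens are interchangeable.

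**Working it through.** **Inputs from section 8.2:** 5% v 80% response; 30-point bound; one-tailed 5% (z = 1.645); 90% power (z = 1.282); 20 per arm. For arms 3 to 7: 65% v 95%, 30 per arm, Fisher's exact test. Arm sizes come from section 4.8.4 and contrasts from section 3.

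**1. The protocol's figure for arms 1 and 2.** The simple unpooled formula is

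n = (1.645 + 1.282)² × (0.05 × 0.95 + 0.80 × 0.20) / (0.75 − 0.30)² = 8.78, so 9 per group.

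At one-sided 2.5% it gives 10.77, so 11 per group. The simple formula is optimistic at such small numbers, so power was also enumerated exactly from the binomial distribution, counting outcomes whose one-tailed 95% lower bound exceeds 30 points:

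| Lower bound | Power stays ≥ 90% from | Power at n = 20 |
|---|---|---|
| Wald | n = 12 | 98.4% |
| Newcombe | n = 15 | 97.1% |
| Wald, continuity-corrected | n = 16 | 96.1% |

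(Wald power is 82.5% at n = 9, 91.1% at n = 10 and 87.4% at n = 11. It is not monotone, hence the wording of the middle column.) None of these rules returns 20. For that hypothetical comparison 20 is more than enough, so this mismatch is conservative and secondary.

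**2. The protocol's figure for arms 3 to 7.** Exact two-sided 5% Fisher power for 65% v 95% with 30 v 30 is 78.8%, which agrees with the stated figure of about 80%. The same calculation is used in step 3.

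**3. The contrasts that arms 1 and 2 serve, four-fold-rise endpoint.** The protocol gives no rates for these contrasts, so the rates here are assumptions. The first pair is the protocol's own for arms 3 to 7. The second takes the 80% of section 8.2 with the same 30-point gap.

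| Contrast | Sizes | 65% v 95% | 50% v 80% |
|---|---|---|---|
| Group 1 v Group 2 | 20 v 20 | 58.9% | 41% |
| Group 1 v Group 5; Group 2 v Group 5 | 20 v 30 | 73.1% to 77.0% | 54% to 55% |

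The ranges for 20 v 30 depend on which arm has the lower rate. With 95% in the better arm, 90% power requires the other arm to fall to about 49% (20 v 20) or 57% (20 v 30, with the lower rate in the arm of 20).

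**4. Precision if both arms respond at 80%.** Half-width of the 95% confidence interval for the difference:

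- 20 v 20: 1.96 × √[0.16 × (1/20 + 1/20)] = 0.248, or 24.8 points
- 20 v 30: 1.96 × √[0.16 × (1/20 + 1/30)] = 0.226, or 22.6 points

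**5. The concentration outcome.** A two-sample t test at two-sided 5% reaches 80% power for a difference d of 0.909 SD (20 v 20) or 0.825 SD (20 v 30) in log concentration. The protocol gives no SD. Assuming 0.3 to 0.5 on the log10 scale, the detectable ratio 10^(d × SD) is 1.87 to 2.85 for 20 v 20 and 1.77 to 2.59 for 20 v 30.

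**The case against.** The best alternative reading is that the 5% is a benchmark rather than an arm. Section 8.6 compares each arm with its own titre before vaccination, and section 3 has a single-arm objective for Group 1. That may be where the 5% came from, but it does not rescue the calculation. A four-fold rise from baseline already incorporates baseline, so the pre-vaccination sample has no response rate of its own. Section 8.2 also describes a difference between two groups with a number per group, and Group 2 has no single-arm objective.

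Three further points carry weight. First, the method cited for the figure of 20 cannot be inspected here, and the rules tried span 9 to 16, so the failure to reproduce 20 is a side issue. Second, the low power figures depend on assumed rates. What the protocol establishes is that power for these contrasts is unstated, and a large enough true difference would bring it to 90%. Third, the protocol claims no equivalence between formulations. Its aim of showing no reduction in immunogenicity concerns co-administration, so the caution about non-significant results guards against a misreading and corrects no statement in the text. None of this supplies a contrast to which the stated 90% applies.

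**Conclusion.** The concern holds. The 90% power and the stated basis for 20 per arm apply to no comparison that arms 1 and 2 can enter. This follows from sections 3, 4.8.4 and 8.2, Table 3 and Appendix A alone and needs no assumed rates. How far real power falls short does depend on assumptions. For a 30-point difference on the four-fold-rise endpoint it is 41% to 59% for Group 1 v Group 2 and 54% to 77% for the two contrasts with Group 5, under the rate pairs shown. Those figures do not describe the concentration outcome, for which the detectable difference is 0.91 or 0.83 SD. The sample size itself need not change. The error lies in what section 8.2 says it delivers, and it should be corrected.

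**What to change.** In section 8.2:

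- Remove the 5% reference basis and the 90% power for arms 1 and 2, and keep 20 per arm.
- Name the contrasts these arms serve (Group 1 v Group 2, Group 1 v Group 5, Group 2 v Group 5) and give the power or precision for each, with endpoint and assumed rates stated. For the four-fold-rise endpoint this could be 59% and 73% to 77% if 65% v 95% is assumed, or half-widths of about 25 and 23 points if both arms respond at 80%.
- Add the detectable difference in log concentration, with the SD assumed and its source.
- Say that a non-significant result in these contrasts does not show equivalence.
- Align the opening objective with section 3. Reconcile the synopsis at the same time: it labels the antimalarial comparison as Group 2 v Group 3 and Group 4 v Group 6, whereas section 3 has Group 3 v Group 4 and Group 5 v Group 6.

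The cost is a rewording and a less favourable stated power for arms 1 and 2. No participants are added, and no arm or analysis changes.

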8.3 Inclusion in Analysis

All patients who received at least one dose of vaccine will be included in the safety analyses. Patients lost to follow-up before the completion of the follow-up period assessments will be censored at the last day seen.

Immunology analyses

Given the incidence of malaria in the study area, it is highly unlikely that any volunteer will become infected with any *Plasmodium* species during the trial. However, to exclude the remote possibility that a participant becomes infected we will screen participants for malaria at screening, Month 0, Month 1, Month 2, Month 3, and Month 6. The malaria screen consists of a blood film which is read immediately in the hospital laboratory. The result will be available in <30 min. Subjects positive for malaria at screening or Month 0 are excluded from participation in the study and will not be enrolled or vaccinated. Subjects positive for malaria at Month 1 or Month 2 will be withdrawn from further vaccinations. In the remote scenario that a volunteer becomes parasitaemic during the study results obtained from that point in time onward will be confounded by the immune response to the natural infection. Immunology results obtained during and after an episode of parasitaemia will be excluded from the immunology analysis. The results can be included in the safety analysis.

8.4 Overall plan

Both intention-to-treat and per-protocol analyses will be carried out.

- In the intention-to-treat analysis, every participant randomized in the study (who receive the correct or incorrect study agent, one or more doses, and complete or incomplete doses) will be analysed, except if he/she did not receive any dose of the study vaccine or if no post-randomization data was collected for this participant.
- The per-protocol analysis will compare participants according to the study agent actually received and will include only those participants who satisfied the inclusion/exclusion criteria, followed the protocol, and received three complete, correct doses. The following non-compliant participants will be excluded:
 - o Participants included without meeting at least one inclusion criterion
 - o Participants included despite meeting at least one exclusion criterion
 - o Participants found non-compliant with the blood sampling schedule
 - o Participants vaccinated with the wrong study agent (non-compliance with the randomization code)

- Participants excluded from the intention-to-treat analysis.

No interim analysis is planned.

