4.8.7 Blood tests

Blood will be drawn at the time points indicated in the schedule of procedures (Appendix A) and the following laboratory assays performed:

At screening:

- Haematology: haemoglobin [Hb], leukocytes [white blood cells; WBC] and platelets [PLT].
- Biochemistry: alanine aminotransferase [ALT], aspartate aminotransferase [AST] and creatinine [CREA].

- Diagnostic serology: HBsAg, HCV antibodies, HIV antibodies (Counselling will be given prior to testing blood for these blood-borne viruses)
- Parasite microscopy*

At M0, D0: Parasite microscopy*, Haematology: Hb, WBC, PLT, Biochemistry: ALT, AST, CREA, anti-CS antibody; Pharmacokinetics** (piperazine and primaquine drug levels will be assessed if additional data are required)

At M0, D1: Pharmacokinetics** (piperazine and primaquine drug levels)

At M0, D2: Pharmacokinetics** (piperazine drug levels)

At M0, D7: Haematology: Hb, WBC, PLT; Biochemistry: ALT, AST, CREA; Pharmacokinetics** (piperazine drug levels)

At M1, D0: Parasite microscopy*, anti-CS antibody; Pharmacokinetics** (piperazine drug levels)

At M1, D1: Pharmacokinetics** (piperazine and primaquine drug levels)

At M1, D2: Pharmacokinetics** (piperazine drug levels)

At M1, D7: Haematology: Hb, WBC, PLT; Biochemistry: ALT, AST, CREA; Pharmacokinetics** (piperazine drug levels)

At M2, D0: Parasite microscopy*, anti-CS antibody; Pharmacokinetics** (piperazine drug levels)

At M2, D1: Pharmacokinetics** (piperazine and primaquine drug levels)

At M2, D2: Pharmacokinetics** (piperazine drug levels)

At M2, D7: Haematology: Hb, WBC, PLT; Biochemistry: ALT, AST, CREA; Pharmacokinetics** (piperazine drug levels)

At M3: Parasite microscopy*, Haematology: Hb, WBC, PLT; Biochemistry: ALT, AST, CREA; anti-CS antibody

At M6: Parasite microscopy*, anti-CS antibody

* In the unexpected event that volunteers are found to be parasitaemic during screening, baseline or during vaccination or follow-up visits they will be treated according to the most up-to-date government guidelines. If at screening or baseline, these volunteers will be excluded from participation in the study. If at Month 1 or Month 2 vaccination days, these volunteers will be withdrawn from further study vaccination.

** Samples for pharmacokinetics will only be taken for subjects in Groups 4 and 6. Additional drug level assessment for Primaquine will be done if additional data are required

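### The per-protocol set in section 8.4 requires three doses whatever the time point or arm, so early per-protocol antibody results depend on later doses and Group 7 cannot qualify

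*Protocol*

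**What the plan says.** Section 8.4 states that "Both intention-to-treat and per-protocol analyses will be carried out" and ranks neither above the other. The intention-to-treat set takes in randomized participants "who receive the correct or incorrect study agent, one or more doses, and complete or incomplete doses) will be analysed", apart from those with no dose or no post-randomization data. The per-protocol set is to "include only those participants who satisfied the inclusion/exclusion criteria, followed the protocol, and received three complete, correct doses". There is one such definition, with no variant by time point or by arm.

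Section 4.2 makes anti-CS antibody primary at four times. For Groups 1 to 6 the first two are "one month after the first dose (at Study month 1), one month after the second dose (at Study month 2"); Months 3 and 6 follow. Section 4.8.7 schedules these two samples on vaccination days: "At M1, D0: Parasite microscopy*, anti-CS antibody" and "At M2, D0: Parasite microscopy*, anti-CS antibody".

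Table 3 and Appendix A give Group 7 vaccine at Months 0 and 2 only.

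Section 7.2 says: "Individual study participants who present at least one of the following stopping rules for individual subjects will be withdrawn from further vaccination". The triggers include certain persistent Grade 3 events, vaccine-related serious events and acute allergic reactions. Section 4.11 allows a participant who stops vaccine to remain in follow-up.

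**The concern.** A per-protocol result should describe people who complied up to the measurement. Under a whole-course rule, someone in Groups 1 to 6 who received dose 1 correctly, gave a valid Month 1 sample and then missed dose 2 or 3 is left out of the Month 1 per-protocol result. The reason for leaving them out cannot have affected that sample. If later doses are missed partly because of reactions to earlier ones, and reactions are related to antibody response, the retained group is a selected one.

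This matters most for Group 3 v Group 4 and Group 5 v Group 6, which address whether the antimalarials reduce immunogenicity. There a per-protocol result that supports the intention-to-treat result carries weight. The protocol contains a possible route to differential selection. Section 4.7.3 lists gastrointestinal upset and headache among the side effects of DHA-PIP, and both are solicited general events. Rule 7.2(b) on Grade 3 systemic solicited events does not require that the event be related to vaccine.

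The same sentence has a more certain consequence for Group 7. Read literally, it leaves that arm with no per-protocol participants, although Group 6 v Group 7 is a stated objective.

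**Working it through.** **1. Doses scheduled before each sample, against the rule** (section 4.2, section 4.8.7, Appendix A)

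| Sample | Groups 1-6: doses before sample | Group 7: doses before sample | Doses required by 8.4 |
|---|---|---|---|
| Month 1 | 1 | 1 | 3 |
| Month 2 | 2 | 1 | 3 |
| Month 3 | 3 | 2 | 3 |
| Month 6 | 3 | 2 | 3 |

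For Groups 1 to 6 the rule fits Months 3 and 6. It asks for two doses too many at Month 1 and one too many at Month 2. For Group 7 it cannot be met at any time.

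**2. The plan's own power figure.** Section 8.2 gives about 80% power for 65% v 95% with 30 per group, Fisher's exact test, 5% level. Exact enumeration of the two-sided test gives 0.788, so the figure reproduces.

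**3. Precision.** The protocol states no missed-dose rate, so q, the chance of missing each later dose, is an assumption. The number completing all three doses is 30 × (1 − q)².

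- q = 3%: 30 × 0.97² = 28.2, about 28 per group; power 0.742.
- q = 5%: 30 × 0.95² = 27.1, about 27 per group; power 0.715.
- q = 10%: 30 × 0.90² = 24.3, about 24 per group; power 0.706.

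A set defined by time point would keep all 30 at Month 1 and 30 × (1 − q) at Month 2, for example 28.5 at q = 5%. The power figures are jagged because Fisher's test is discrete: power is 0.729 at 26 v 26, higher than at 27 v 27. A steadier measure is the standard error, which grows by √(30/27) = 1.054, about 5%, when 27 rather than 30 remain in each arm.

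**4. Bias on the geometric mean.** Assume that log10 titre has SD σ = 0.5, and that a fraction s stops at the upper tail of a normal variable with correlation ρ to log titre. With z the 1 − s normal quantile and φ the normal density,

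retained geometric mean ratio = 10^(−ρ σ φ(z)/(1 − s)).

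For s = 10%: z = 1.2816, φ(z) = 0.1755, and φ(z)/(1 − s) = 0.195.

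- ρ = 0: ratio 1, no bias.
- ρ = 0.2: 10^(−0.0195) = 0.956, about 4% low.
- ρ = 0.5: 10^(−0.0488) = 0.894, about 11% low.

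For s = 3% (z = 1.881, φ(z)/(1 − s) = 0.070), the same correlations give 1.6% and 3.9%.

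For scale, at σ = 0.5 the 95% margin on a geometric mean ratio with 30 v 30 is 10^(1.96 × 0.5 × √(2/30)) = 10^0.253 = 1.79-fold either way.

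**5. Bias on the responder scale.** Take a true response of 80% (the vaccine-group assumption in section 8.2), 5% of non-responders missing later doses, and a higher assumed rate in responders.

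- 5% in responders: 80.0%, no bias.
- 10%: (0.8 × 0.90)/(0.8 × 0.90 + 0.2 × 0.95) = 0.720/0.910 = 79.1%.
- 20%: 0.640/0.830 = 77.1%, about 3 points low.

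**The case against.** **Intention-to-treat keeps the samples.** A reader might infer that the Month 1 and Month 2 primary results as a whole are selected and that valid data are thrown away. The documents do not support this. Section 8.4 also requires the intention-to-treat analysis, in which a participant with one dose and a Month 1 sample stays, and it does not make per-protocol primary. This objection stands and confines the point to the per-protocol analysis.

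**The text does not say that the set applies at every time point, and an SAP may refine it.** True, and time-point sets are often left to an SAP. But the protocol is not silent: it states a dose rule without qualification, and an SAP that follows it inherits the problem. A sensible analyst would probably read the rule for Group 7 as all scheduled doses, but that is not what it says.

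**A fixed completer set is a legitimate choice.** It lets the Month 1, 2, 3 and 6 profile describe the same people. That is a fair reason to show it as a supplement, but it does not make it a measure of compliance at Month 1.

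**Differential stopping is not documented.** Also true. The holding rules are narrow, section 4.7.3 describes DHA-PIP as very well tolerated, no stopping rate is given, and section 8.2 plans replacement of withdrawn participants where possible. A reader might infer that the antimalarials will distort the early contrasts. The protocol shows only a possible route, not that this will happen.

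**Conflict with section 8.3.** That section says "Immunology results obtained during and after an episode of parasitaemia will be excluded from the immunology analysis", and one might read this as contradicting 8.4, which also drops earlier results. It does not: 8.3 can govern all immunology results and 8.4 the per-protocol set in addition. Section 8.3 also calls infection remote.

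**Conclusion.** The point holds for the per-protocol analysis. As written, section 8.4 makes the Month 1 and Month 2 per-protocol antibody results in Groups 1 to 6 depend on doses due at or after the sample. It also leaves Group 7 with no per-protocol participants, and so no per-protocol Group 6 v Group 7 comparison. The Group 7 consequence follows from the text alone and needs no assumption.

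The size of the selection effect cannot be derived from the protocol. It is nil if stopping is unrelated to titre. Under the assumed inputs (10% stopping in one arm, correlation 0.2 to 0.5, log10 SD 0.5) it is about 4% to 11% on the geometric mean, well inside the roughly 1.8-fold margin for a 30 v 30 comparison. Under the assumed missed-dose rates it reaches about 3 points on the responder scale. The loss of precision is modest and depends equally on an assumed rate. The definition should be corrected because the rule is wrong for its purpose and the correction is cheap, not because a large bias has been shown.

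**What to change.** In section 8.4, and in the SAP, replace the three-dose requirement with a definition for each antibody time point: eligible participants, compliant up to that time point, who correctly received every dose scheduled for their own group before it and who have the antibody sample for it. Add that a later missed dose does not remove earlier results. For Group 7 this means one dose for Months 1 and 2, and both doses for Months 3 and 6.

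The cost is a sentence or two. The per-protocol number will differ by time point and must be shown in each table. If the same people are wanted throughout the antibody profile, a fixed completer set, defined by each group's own schedule, can be kept as a sensitivity analysis.
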